6.10.3 Actions after Discontinuation

All subjects who discontinue study treatment due to a report of an AE must be followed and provided appropriate medical care until their signs and symptoms have remitted or stabilized.

For subjects who choose to withdraw consent or who are discontinued for non-compliance prior to completing the study, every possible effort should be made by the Investigator to assure there is a final visit that includes all examinations listed for the Week 8 / Early Termination Visit.

6.10.4 Discontinuation of the Entire Study

The entire study may be discontinued at a given site (by the Investigator or Aerie / Aerie representative) or at all sites by Aerie. Prompt, written notice of reasonable cause to all other relevant parties (Aerie or Investigator) is required. Prompt notice to the IRB and to regulatory authorities is also required.

6.10.5 Completed Study

The study is completed when the planned enrollment has been completed, and all the enrolled subjects have completed the study. An Aerie representative will be in communication with the investigational sites regarding enrollment.

6.11 Appropriateness of Measurements

The ophthalmic and systemic measures included in this study are consistent with standard of care.

7. STUDY ACTIVITIES

A detailed Schedule of Visits and Procedures is provided in [Table 1](#). Subjects should be scheduled at approximately the same time of day \pm 60 mins in the morning (ideally at or before 10:00 local time) for each visit to ensure that ultrasound pachymetry is completed before noon (local time).

7.1 Screening Visit (Day -8 to -1)

- Informed consent
- Inclusion and exclusion criteria
- Demographics
- Medical, ophthalmic, and surgical history
- Prior or concomitant medication review
- Vital signs (heart rate and blood pressure only)
- Ocular symptoms and AE review for both eyes
- BCVA using the ETDRS method and following manifest refraction for both eyes
- Anterior segment biomicroscopic examination of both eyes
- CCT will be measured by ultrasound pachymetry in both eyes
 - Note: Ultrasound pachymetry should be performed at approximately the same time of day for all visits (\pm 60 minutes) and always before noon (local time)
- IOP in both eyes
- Dilated Ophthalmoscopy in both eyes
- Tomography (Pentacam[®]) for both eyes (at selected sites only) – may be performed prior to ophthalmoscopy while the subject is dilating

7.2 Treatment Period

7.2.1 Baseline (Day 1) Procedures

- Inclusion and exclusion criteria
- Visual Function and Corneal Health Status (V-FUCHS) patient reported visual disability questionnaire ([Wacker 2018](#))
- Medical, ophthalmic, and surgical history
- Concomitant medication review
- Vital signs (heart rate and blood pressure only)

- Urine pregnancy test (WOCBP only)
- Ocular symptoms and AE review for both eyes
- BCVA using the ETDRS method and following manifest refraction for both eyes
- Anterior segment biomicroscopic examination of both eyes
- CCT will be measured by ultrasound pachymetry in both eyes
 - Note: Ultrasound pachymetry should be performed at approximately the same time of day for all visits (\pm 60 minutes) and always before noon (local time)
- IOP in both eyes
- Ophthalmoscopy without dilation in both eyes
- Tomography (Pentacam[®]) for both eyes (at selected sites only)
- Study eye determination (See Section 4.4)
- Randomization
- Eye drop instruction and demonstration for the study eye
- Dispensing of study medication, Study Artificial Tears (if randomized to the QD dosing arm), and Protocol Approved Artificial Tears

7.2.2 Week 2 (Day 14 \pm 3) Procedures

- Concomitant medication review
- Ocular symptoms and AE review for both eyes
- BCVA using the ETDRS method and following manifest refraction for both eyes
- Anterior segment biomicroscopic examination of both eyes
- CCT will be measured by ultrasound pachymetry in both eyes
 - Note: Ultrasound pachymetry should be performed at approximately the same time of day for all visits (\pm 60 minutes) and always before noon (local time)
- IOP in both eyes
- Ophthalmoscopy without dilation in both eyes
- Tomography (Pentacam[®]) for both eyes (at selected sites only)

7.2.3 Week 4 (Day 28 ± 3) Procedures

- Visual Function and Corneal Health Status (V-FUCHS) patient reported visual disability questionnaire (Wacker 2018)
- Concomitant medication review
- Ocular symptoms and AE review for both eyes
- BCVA using the ETDRS method and following manifest refraction for both eyes
- Anterior segment biomicroscopic examination of both eyes
- CCT will be measured by ultrasound pachymetry in both eyes
 - Note: Ultrasound pachymetry should be performed at approximately the same time of day for all visits (\pm 60 minutes) and always before noon (local time)
- IOP in both eyes
- Ophthalmoscopy without dilation in both eyes
- Tomography (Pentacam[®]) for both eyes (at selected sites only)
- Dispensing of study medication, Study Artificial Tears (if randomized to the QD dosing arm), and Protocol Approved Artificial Tears (if needed)
 - Note: At the Week 4 Visit, any subject randomized to netarsudil QD who, in the opinion of the Investigator, has not responded adequately to treatment, may have their netarsudil dosing frequency increased to BID for the remainder of the study. The subject should be re-trained on their new dosing regimen, if applicable.

7.2.4 Week 8 (Day 56 ± 3) or Early Termination Procedures

- Visual Function and Corneal Health Status (V-FUCHS) patient reported visual disability questionnaire (Wacker 2018)
- Concomitant medication review
- Vital signs (heart rate and blood pressure)
- Urine pregnancy test (WOCBP only)
- Ocular symptoms and AE review for both eyes
- BCVA using the ETDRS method and following manifest refraction for both eyes

- Anterior segment biomicroscopic examination of both eyes
- CCT will be measured by ultrasound pachymetry in both eyes
 - Note: Ultrasound pachymetry should be performed at approximately the same time of day for all visits (\pm 60 minutes) and always before noon (local time)
- IOP in both eyes
- Dilated ophthalmoscopy in both eyes
- Tomography (Pentacam[®]) for both eyes (at selected sites only) – may be performed prior to ophthalmoscopy while the subject is dilating

The Week 8 Visit will be the final visit, and the subject should be thanked for their participation in the study.

7.2.5 Unscheduled Visits

An unscheduled visit may be any visit to the Investigator other than the specific visits specified in the protocol as possibly required for the subject's ophthalmic condition.

The Investigator will perform all procedures necessary to evaluate the study participant at these visits and record any AEs in the CRF.

8. QUALITY CONTROL AND ASSURANCE

The progress of the study will be monitored by on-site, written, and telephone communications between personnel at the Investigator's site and the Study Monitor. The Investigator will allow the Sponsor or designee to inspect all CRFs, subject records (source documents), signed consent forms, study medication records (receipt, storage, preparation, and disposition), and regulatory files related to this study.

9. PLANNED STATISTICAL METHODS

9.1 General Considerations

Continuous study assessments will be summarized by treatment and time point (as applicable) using descriptive statistics (n, mean, median, standard deviation, minimum, and maximum). Categorical study assessments will be summarized by treatment and visit (as applicable) using frequency counts and percentages. Hypothesis testing, unless otherwise indicated, will be performed at a 2-sided 0.10 significance level. Where applicable, 2-sided 90% and 95% CIs will be reported. All p-values will be displayed to four decimal places, with p-values less than 0.0001 presented as '<0.0001' and p-values greater than 0.9999 presented as '>0.9999'. Difference between netarsudil QD and netarsudil BID will be calculated as netarsudil QD – netarsudil BID.

All study data will be listed by treatment, subject and time point (as applicable).

Statistical methods will be more fully described in a separate Statistical Analysis Plan.

9.1.1 Unit of Analysis

Safety endpoints will be analyzed for both eyes. For efficacy endpoints, the primary unit of analysis will be the study eye defined based on CCT of at least 600 μm evaluated by ultrasound pachymetry. If both eyes qualify based on CCT and enrollment criteria, the study eye will be the eye with the thinner cornea at the baseline. Qualified fellow eyes may also be summarized.

9.1.2 Missing Data and Intercurrent Events

The primary analysis will be completed with available data per subject from the mITT population. Robustness analyses will also be presented based on the multiple imputation methodology under different assumptions of missingness and intercurrent events (at random and not at random), using last observation carried forward (LOCF), and using the per protocol population with available data per subject.

Intercurrent events will be primarily handled in the following manner:

1. Discontinuation of study medication and non-optimal compliance will be ignored, values measured after discontinuation of study medication or regardless of compliance will be used in the analyses [treatment policy strategy].
2. Withdrawal due to lack of efficacy or adverse events: missing data will be singly imputed as the worst within subject observation prior to the intercurrent event [hypothetical strategy].
3. Missing data without withdrawal or withdrawal due to reasons other than lack of efficacy or adverse events: missing data will be imputed employing Multiple Imputation (MI) using randomized treatment-based Markov Chain Monte Carlo (MCMC) methodology to impute non-monotone missing data and regression methodology to impute monotone missing data [hypothetical strategy].

9.1.3 Multiplicity Considerations

Adjustments for multiplicity will not be made in this early phase trial.

9.2 Hypotheses

H_{01} : The mean change from baseline CCT by ultrasound pachymetry in study eyes treated with netarsudil QD at Week 4 = 0.

H_{11} : The mean change from baseline CCT by ultrasound pachymetry in study eyes treated with netarsudil QD at Week 4 \neq 0.

H_{02} : The mean change from baseline CCT by ultrasound pachymetry in study eyes treated with netarsudil BID at Week 4 = 0.

H_{12} : The mean change from baseline CCT by ultrasound pachymetry in study eyes treated with netarsudil BID at Week 4 \neq 0.

9.3 Determination of Sample Size

This study is not powered to detect a pre-stated efficacy signal, but rather will be used to inform the design and power for any possible future studies. With a sample size of up-to 20 subjects per treatment group, the precision of the point estimate of mean change from baseline in CCT, as measured by the half-width of the two-sided 90% confidence interval (CI), will be approximately 1/2.7 of the standard deviation (SD) of the change from baseline, yielding 90% confidence that the true mean change from baseline is within \pm SD/2.7 μ m of the observed mean change from baseline. That is, if the SD of the change from baseline is 60 μ m, then the half-width of the two-sided 90% CI would be $60 \mu\text{m} \times 1/2.7 = 22.2 \mu\text{m}$, yielding 90% confidence that the true mean change from baseline is within $\pm 22.2 \mu\text{m}$ of the observed mean change from baseline.

With a sample size of up-to 20 subjects within a treatment group, the study will have 80% power to reject H_{01} or H_{02} and in favor of H_{11} or H_{12} respectively and demonstrate a statistically significant mean change from baseline, assuming the true effect size (mean change / SD) is 0.577 or larger (e.g., assuming the true mean change from baseline is 34.6 μ m and the standard deviation is 60 μ m), a one sample t-test and a two-sided alpha = 0.10.

With a sample size of up-to 20 subjects per treatment group, the study will have 95% confidence of ruling out AEs with true incidence rates of 13.9% or higher within each treatment group. That is, with up-to 20 subjects in a treatment group, if an AE of a specific type is not observed, then with 95% confidence, the true incidence rate of that adverse event is less than 13.9%.

Similarly, with a sample size of up-to 40 subjects combined over treatment groups, the study will have 95% confidence of ruling out AEs with true incidence rates of 7.2% or higher within each treatment group. That is, with up-to 40 subjects in a treatment group, if an AE of a specific type is not observed, then with 95% confidence, the true incidence rate of that adverse event is less than 7.2%.

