9.8.2 Primary Efficacy Analyses

The primary comparisons in this trial will be within a treatment group on the mean change from baseline CCT to Week 4/Day 28 (Visit 4) for each of netarsudil QD and BID.

The primary efficacy endpoint change from baseline CCT will be summarized descriptively (n, mean, standard deviation, median, min, and max) and analyzed primarily using one-sample t-tests; comparisons between treatment groups will be completed using two-sample t-tests. Sensitivity analyses will be completed using Wilcoxon signed-rank tests within a treatment group, Wilcoxon rank sum tests between treatment groups and an ANCOVA model with terms for baseline CCT value, treatment. The least squares mean will be presented for each treatment group from the model together with two-sided p-values and 90 and 95% confidence intervals around the change from baseline within each treatment group. Comparisons between treatment groups on the change from baseline CCT will also be made including the least squares mean difference and corresponding two-sided p-values and 90 and 95% confidence intervals.

The primary analysis will use the mITT population with available data per subject. Robustness analyses will also be presented based on the multiple imputation methodology under different assumptions of missingness and intercurrent events (at random and not at random), using last observation carried forward (LOCF), and using the per protocol population with available data per subject.

Intercurrent events will be primarily handled in the following manner:

1. Discontinuation of study medication and non-optimal compliance will be ignored, values measured after discontinuation of study medication or regardless of compliance will be used in the analyses [treatment policy strategy].
2. Withdrawal due to lack of efficacy or adverse events: missing data will be singly imputed as the worst within subject observation prior to the intercurrent event [hypothetical strategy].
3. Missing data without withdrawal or withdrawal due to reasons other than lack of efficacy or adverse events: missing data will be imputed employing Multiple Imputation (MI) using randomized treatment-based Markov Chain Monte Carlo (MCMC) methodology to impute non-monotone missing data and regression methodology to impute monotone missing data [hypothetical strategy].

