## 5. Sample Size and Power Considerations

This study is not powered to detect a pre-stated efficacy signal, but rather will be used to inform the design and power for any possible future studies. With a sample size of up-to 20 subjects per treatment group, the precision of the point estimate of mean change from baseline in CCT, as measured by the half-width of the two-sided 90% confidence interval (CI), will be approximately  $1/2.7$  of the standard deviation (SD) of the change from baseline, yielding 90% confidence that the true mean change from baseline is within  $\pm SD/2.7 \mu\text{m}$  of the observed mean change from baseline. That is, if the SD of the change from baseline is  $60 \mu\text{m}$ , then the half-width of the two-sided 90% CI would be  $60 \mu\text{m} \times 1/2.7 = 22.2 \mu\text{m}$ , yielding 90% confidence that the true mean change from baseline is within  $\pm 22.2 \mu\text{m}$  of the observed mean change from baseline.

With a sample size of up-to 20 subjects within a treatment group, the study will have 80% power to reject  $H_{01}$  or  $H_{02}$  and in favor of  $H_{11}$  or  $H_{12}$  respectively and demonstrate a statistically significant mean change from baseline, assuming the true effect size (mean change / SD) is 0.577 or larger (e.g. assuming the true mean change from baseline is  $34.6 \mu\text{m}$  and the SD is  $60 \mu\text{m}$ ), a one sample t-test and a two-sided alpha = 0.10.

With a sample size of up-to 20 subjects per treatment group, the study will have 95% confidence of ruling out AEs with true incidence rates of 13.9% or higher within each treatment group. That is, with up-to 20 subjects in a treatment group, if an AE of a specific type is not observed, then with 95% confidence, the true incidence rate of that adverse event is less than 13.9%.

Similarly, with a sample size of up-to 40 subjects combined over treatment groups, the study will have 95% confidence of ruling out AEs with true incidence rates of 7.2% or higher within each treatment group. That is, with up-to 40 subjects in a treatment group, if an AE of a specific type is not observed, then with 95% confidence, the true incidence rate of that AE is less than 7.2%.

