## 12.2 Primary Efficacy Analysis

The primary comparisons in this trial will be within a treatment group on the mean change from baseline CCT by ultrasound pachymetry at Week 4/Day 28 (visit 4) for each of netarsudil QD and BID. The summary will be provided for the study eye. The primary efficacy endpoint change from baseline in CCT will be summarized using continuous descriptive statistics and analyzed primarily using one-sample t-tests by treatment group; comparisons between treatment groups (QD – BID) will be completed using two-sample t-tests. Sensitivity analyses will be completed using Wilcoxon signed-rank tests within a treatment group, Wilcoxon rank sum tests between treatment groups and an analysis of covariance (ANCOVA) model with terms for baseline CCT value and treatment.

The mean change from baseline in CCT for each treatment group along with 2-sided p-values and 90% and 95% CIs around the change from baseline within each treatment group for the mean from one-sample t-test will be presented. The mean difference in change from baseline between treatment groups along with 2-sided p-values and 90% and 95% CIs for the mean differences between treatment groups from two-sample t-test will be presented. P-values from Wilcoxon signed-rank test within each treatment group, and Wilcoxon rank-sum test between treatment groups will be presented. The least squares (LS) mean for each treatment group along with 2-sided p-values and 2-sided 90% and 95% CIs around the change from baseline within each treatment group will be presented from the ANCOVA model.

Comparisons between treatment groups on the change from baseline in CCT will also be made including the LS mean difference and the corresponding 2-sided p-values and 90% and 95% CIs.

Example SAS® code for the primary efficacy analysis on change from baseline (CHG\_CCT):

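### The stated 90% precision of SD/2.7 (22.2 µm) matches a normal quantile; the planned one-sample t interval at 20 per group gives SD/2.59 (23.2 µm), a minor correction

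*Protocol*

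**What the plan says.** Protocol 9.3 opens its sample size justification with precision. It begins "With a sample size of up-to 20 subjects per treatment group, the precision of the point estimate of mean change from baseline in CCT" and continues that the half-width of the two-sided 90% interval "will be approximately 1/2.7 of the standard deviation (SD) of the change from baseline, yielding 90% confidence". The worked example is conditional ("if the SD of the change from baseline is 60" µm) and arrives at ±22.2 µm. SAP 5 carries the same paragraph, including the confidence claim: "of the standard deviation (SD) of the change from baseline, yielding 90% confidence that the true mean change from baseline is within" plus or minus SD/2.7. Neither document says which quantile was used, or that the SD is treated as known.

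The next paragraph in both places gives 80% power at an effect size of 0.577 and names a one-sample t-test at two-sided alpha 0.10.

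On the analysis, Protocol 9.8.2 says the primary endpoint is "analyzed primarily using one-sample t-tests". SAP 12.2 says where the intervals come from: "90% and 95% CIs around the change from baseline within each treatment group for the mean from one-sample t-test will be presented". Its example code for the within-group analysis is PROC TTEST. Neither document plans a normal-quantile interval.

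**The concern.** The precision figure and the planned interval appear to rest on different distributions. With 20 subjects and an estimated SD, a t interval is visibly wider than a normal one, so a figure from the normal quantile understates the interval that the trial will report. The power statement beside it appears to use t, so two neighbouring paragraphs with the same n, the same error level and the same SD would be using two methods.

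What is at stake is limited but real. Protocol 9.3 says the study is not powered for a pre-stated efficacy signal and is meant to inform later studies. In that setting the expected precision is one of the reasons given for the group size, and it should describe the interval actually planned.

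**Working it through.** **Inputs.** n = 20 per group, stated as a maximum (Protocol 9.3); two-sided 90% confidence (Protocol 9.3); SD of change 60 µm, illustrative (Protocol 9.3); interval from the one-sample t-test (SAP 12.2); effect size 0.577, alpha 0.10 two-sided, t-test (Protocol 9.3).

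**1. Reproducing the stated figure.** Half-width = z(0.95) × SD/√n.
- 1.6449/√20 = 1.6449/4.4721 = 0.3678, which is 1/2.72 and rounds to 1/2.7.
- 60/2.7 = 22.2 µm; without rounding the divisor, 60 × 0.3678 = 22.1 µm.

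**2. The planned interval.** Half-width = t(0.95, n − 1) × SD/√n.
- t(0.95, 19) = 1.7291; 1.7291/4.4721 = 0.3866, which is 1/2.586, or 1/2.59.
- 60 × 0.3866 = 23.2 µm.
- Difference: 23.2 − 22.2 = 1.0 µm; 23.2/22.2 = 1.045, so 4.5% wider.

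**3. Could another t-based quantity give 2.7?** The average realised t half-width uses E[s] = 0.987 SD: 0.987 × 0.3866 = 0.3816, which is 1/2.62, or 22.9 µm. That does not round to 2.7 either. Of the variants tried, only the normal quantile does.

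**4. Confidence carried by mean ± SD/2.7 at n = 20.** √20/2.7 = 1.656.
- SD estimated from the sample: 2 × T₁₉(1.656) − 1 = 88.6%.
- SD known: 2 × Φ(1.656) − 1 = 90.2%.

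**5. Method behind the power statement.** With the noncentral t, 19 df and noncentrality 0.577 × √20, power is 80.0%. A normal formula would need an effect size of only (1.645 + 0.842)/√20 = 0.556 for 80%. So 0.577 is a t-based figure and it is correct.

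**6. What n would give 22.2 µm with a t interval?** At SD 60 µm the t half-width is 22.6 µm at n = 21 and 22.0 µm at n = 22. The gap is thus worth about two subjects per group.

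**7. Fewer evaluable subjects.** Twenty is a maximum and the primary analysis uses available data. The documents give no dropout rate, so these counts are assumptions: the t half-width is 24.6 µm at 18 evaluable and 26.3 µm at 16.

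**The case against.** The strongest reply is that the sentence can be read as true. It expresses precision in terms of the SD of the change and takes that SD as given. With a known SD, ±SD/2.7 carries 90.2%, and a normal approximation is a common planning convention. This stands in part: the 88.6% figure applies only when the SD is the sample SD, and the use of the normal quantile is an inference from the arithmetic. But the known-SD interval is not the one SAP 12.2 plans, the approximation is not labelled, and the adjacent power statement does not use it.

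A second reply is that the text says the figure is approximate. That does not cover the gap, because 2.586 rounds to 2.6 and not to 2.7, and the result is then quoted to a tenth of a micrometre with an explicit 90% attached.

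A third is that the gap is small beside the uncertainty in the SD. This is fair. At a true SD of 60 µm and n = 20, the central 90% range of the realised t half-width is about 16.9 to 29.2 µm (chi-square, 19 df), and the average exceeds the stated value by only 0.7 µm.

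A reader might go further and infer that the trial is undersized, that its power is overstated, or that the reported intervals will be too narrow. The documents support none of these. They set no precision target and do not derive n from 22.2 µm. The 80% power is already t-based. PROC TTEST will produce a proper t interval whatever Protocol 9.3 says. Nor is ±22.2 µm a commitment: it is a conditional illustration, one of several statements in the section alongside power and adverse event rates.

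**Conclusion.** The concern holds as a minor correction. For the planned one-sample t interval with 20 evaluable subjects per group, the two-sided 90% half-width is SD/2.59, or 23.2 µm at the illustrative SD of 60 µm. The stated SD/2.7 and 22.2 µm are about 1.0 µm, or 4.5%, too favourable. The conclusion rests on SAP 12.2 taking the intervals from the t-test. The relative gap does not depend on the value of 60 µm. That the normal quantile is the source is likely but not stated. The sample size, the power statement, the primary test and the interval to be reported all stay as they are.

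**What to change.** In Protocol 9.3 and SAP 5, replace every 1/2.7 with 1/2.59 (twice in each document), SD/2.7 with SD/2.59 (once in each), and 22.2 µm with 23.2 µm (twice in each). Add that this is the half-width of a one-sample t interval with 20 evaluable subjects per group, and that it widens if fewer have Week 4 data. If the sponsor prefers to keep the present figures, the minimum is to label them as a normal approximation that treats the SD as known; this is honest but leaves the precision statement out of step with the planned interval and the power statement.

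The cost is a text edit in two places and a slightly less favourable precision figure. No analysis, program or sample size changes.

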4. STUDY POPULATION SELECTION

4.1 Study Population

A total of approximately 40 subjects will be enrolled into the study at approximately 20 investigational sites within the United States. Subjects will be at least 18 years of age with a diagnosis of FCD, each of whom meets all inclusion criteria and none of the exclusion criteria listed below.

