5.2 Treatments Administered

Subjects will be randomized using a 1:1 allocation ratio to one of two treatment groups:

- Once Daily Netarsudil Dosing Regimen

Study Artificial Tear; one drop, in the study eye in the morning

Netarsudil 0.02% ophthalmic solution; one drop, in the study eye in the evening

- Twice Daily Netarsudil Dosing Regimen

Netarsudil 0.02% ophthalmic solution; one drop, in the study eye in the morning and in the evening

Doses will be self-administered by the study subjects. If the subject is using any another topical ophthalmic drop (e.g., ocular hypotensive medications) at the same time as netarsudil, the subject should be instructed to instill netarsudil first, and wait at least 15 minutes before instilling any additional drops.

For subjects deemed unable to self-administer the doses, a caregiver will be asked to administer the medication. All subjects will administer study medication for approximately 8 weeks.

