### 13.1 Adverse Events

An AE is defined as any untoward medical occurrence associated with the use of a drug in humans, whether or not the event is considered drug-related. An AE can therefore be any unfavorable and unintended sign (eg, an abnormal laboratory finding), symptom, or disease occurring after the first dose of study drug, without any judgment about causality. Any pre-existing medical condition that worsens after first administration of the study drug will also be considered a new AE. The AE reporting period starts from the time the subject signs the informed consent until the subject's last study visit. All AEs will be coded using MedDRA Version 23.0.

A treatment-emergent adverse event (TEAE) is defined as any event that occurs or worsens on or after the first dose of study medication. Adverse events recorded on the eCRF which began prior to treatment and remained unchanged or improved will not be included in the summary tables but will be included in the AE data listings. For all AE summary tables, a third group other than QD and BID dose group will be presented to capture the AEs for those subjects who switched the treatment dose from QD to BID starting from Week

4. The AE that began on or after the switch will be considered treatment emergent to the BID treatment; The AE that began before the switch and continued after the switch will be considered treatment emergent to the QD treatment only; if the AE worsened on or after the switch, the new AE (one with higher severity) would become a TEAE for the BID dose and the original AE would be treatment emergent to the QD dose.

An overall summary will be presented that includes the number of events and the number and percentage of subjects who experienced at least one TEAE, by treatment group. This summary will also include breakdowns of TEAEs further categorized as ocular (study eye and fellow eye separately with TEAEs occurred on both eyes counted towards study eye once and fellow eye once) or non-ocular, TEAEs by maximum severity, TEAEs by maximum relationship to study medication, TEAE by expectedness, serious TEAEs, TEAEs leading to study medication discontinuation, TEAEs leading to death.

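### The 7.2% zero-event adverse-event bound needs 40 subjects, but Protocol 9.3 and SAP 5 claim it for each treatment group of 20

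*Protocol*

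**What the plan says.** Protocol 9.3 closes with two statements about AEs that are not observed. The first concerns up to 20 subjects per group: "the study will have 95% confidence of ruling out AEs with true incidence rates of 13.9% or higher within each treatment group". The second starts from up to 40 subjects combined over the groups, yet concludes that "the study will have 95% confidence of ruling out AEs with true incidence rates of 7.2% or higher within each treatment group". Its explanatory sentence then begins "That is, with up-to 40 subjects in a treatment group". SAP 5 repeats both statements, including "That is, with up-to 40 subjects in a treatment group, if an AE of a specific type is not observed". SAP 15, which lists the changes from the protocol, does not touch this text.

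The group sizes follow from two other places. Protocol 4.1 says "A total of approximately 40 subjects will be enrolled into the study", and Protocol 5.2 says "Subjects will be randomized using a 1:1 allocation ratio to one of two treatment groups". Each group is therefore planned at about 20.

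On efficacy precision, Protocol 9.3 says that the half-width of the 90% confidence interval for mean change in central corneal thickness "will be approximately 1/2.7 of the standard deviation (SD) of the change from baseline", and works this out as 22.2 µm for an SD of 60 µm.

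**The concern.** The section gives two different 95% bounds, 13.9% and 7.2%, for the same quantity: the AE rate within a treatment group when no event is seen. Both cannot hold for a group of 20. The second paragraph also contradicts itself, since it begins with the pooled sample and ends with 40 subjects in one group.

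A reader who takes the last paragraph at its word credits each regimen with about twice the safety precision the design gives. Evaluating the safety of the once-daily and twice-daily regimens is a secondary objective, and Protocol 9.3 says the study is meant to inform later trials, so the precision available per regimen should be stated correctly.

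**Working it through.** **Inputs**
- Subjects per group: up to 20; combined: up to 40 (Protocol 9.3, SAP 5; consistent with Protocol 4.1 and 5.2).
- Events observed: 0. Confidence: 95%. The documents do not state sidedness; the one-sided exact form reproduces both of their figures.

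**Step 1: reproduce the stated figures.** With no events in n subjects, the exact one-sided 95% upper bound solves (1 − p)^n = 0.05, so p = 1 − 0.05^(1/n).
- n = 20: 1 − 0.05^(1/20) = 0.1391, i.e. 13.9%.
- n = 40: 1 − 0.05^(1/40) = 0.0722, i.e. 7.2%.

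Both figures are right for their own n. Other forms give, at n = 20 and n = 40: two-sided exact 16.8% and 8.8%; rule of three 15.0% and 7.5%; one-sided Wilson 11.9% and 6.3%; two-sided Wilson 16.1% and 8.8%. None gives 7.2% at n = 20.

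**Step 2: apply 7.2% to a group of 20.**
- P(no event) = 0.928^20 = 0.2244.
- P(at least one event) = 1 − 0.2244 = 0.7756.
- Group size needed for a 7.2% bound: ln 0.05 / ln 0.928 = 40.1, about 40 in that one group.

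**Step 3: can zero events in all 40 bound each group at 7.2%?** Let the group rates be p1 and p2. Then P(0 of 40) = (1 − p1)^20 × (1 − p2)^20. The largest p1 that still leaves this probability at 5% is p1 = 1 − 0.05^(1/20) / (1 − p2).

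| Rate in the other group | 95% limit for this group |
|---|---|
| 0% | 13.9% |
| 2% | 12.2% |
| 5% | 9.4% |
| 7.2% | 7.2% |

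The limit depends on the unknown rate in the other group, and without an assumption about that rate it is 13.9%. For example, rates of 13.9% and 0% average 6.95%, below 7.2%, and all 40 subjects are event-free with probability 0.861^20 = 5.0%.

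**Step 4: what 7.2% does bound.** A geometric mean cannot exceed an arithmetic mean, so (1 − p1)^20 × (1 − p2)^20 ≤ (1 − (p1 + p2)/2)^40. If the average rate is 7.2% or more, P(0 of 40) is at most 0.928^40 = 0.0503, i.e. 5% apart from rounding of 7.2%. The bound is valid for the rate averaged over two equal groups.

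**Minor check: the half-width at n = 20, SD 60 µm.**
- Stated: 60/2.7 = 22.2 µm.
- Normal quantile: 1.6449/√20 = 1/2.72, giving 22.1 µm.
- t with 19 df: 1.7291/√20 = 0.3866 = 1/2.59, giving 23.2 µm if 60 is the observed SD. If 60 is the true SD, the expected t half-width is 0.9869 × 23.20 = 22.9 µm.
- Coverage of ±22.2 µm is 90.2% if 60 is the true SD, and its confidence is 88.6% if 60 is the sample SD.

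The power statement is t-based and reproduces: effect size 0.577, n = 20, two-sided 0.10 gives 0.8001.

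**The case against.** Nothing is miscalculated, and the second paragraph opens by saying that the 40 are combined, so the intended meaning can be recovered. This is right. The error lies in what the number is attached to, which is why new wording is enough.

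A stronger argument is that 77.6% is a worst case. The sentence conditions on all 40 subjects. With one group at a true rate of 7.2%, the chance of at least one event among the 40 is 1 − 0.2244 × (1 − p2)^20: 77.6% if the other group's rate is 0%, 85.0% at 2%, 92.0% at 5%, 95.0% at 7.2% and 97.3% at 10%. Under a common rate the per-group claim would be true. The range is correct, but it does not rescue the sentence. A confidence statement must hold whatever the unknown rates are, so its level is the minimum over the other group's rate, and that is 77.6%. The documents nowhere assume a common rate; the study compares two dosing frequencies and summarizes AEs by group. The explanatory sentence about 40 subjects in one group is wrong under any assumption.

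The consequences are small. AEs are only counted and tabulated, and no sample size, test or output depends on 7.2%.

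On the half-width, the plan says approximately, and if 60 µm is read as the true SD the stated interval has its 90% coverage. That point is a matter of consistency with the t-based analysis, not an error of substance.

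**Conclusion.** The statement is wrong as written in both documents. The 7.2% bound holds for the AE rate averaged over the combined cohort of 40. Within a group of 20 the bound is 13.9%, about twice as large, and the guaranteed confidence of the per-group 7.2% claim is 77.6% instead of 95%. This rests on groups of 20, zero observed events, the one-sided exact binomial bound that reproduces the plan's own figures, and no assumption that the two groups share a rate. With fewer than 20 in a group, the per-group bound would exceed 13.9%.

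The text should be corrected, but nothing in the planned analysis depends on it. The conclusion does not rest on the half-width remark, where the gap is about 1 µm.

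**What to change.** Replace the final paragraph of Protocol 9.3 and of SAP 5 with wording such as: If no AE of a given type is seen among up to 40 subjects in the two groups together, its incidence in the combined cohort is below 7.2% with 95% confidence; for each randomized group of up to 20 the corresponding bound is still 13.9%, reached with 20 subjects.

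The term randomized group is safer than regimen, because once-daily subjects may move to twice-daily dosing at Week 4 and SAP 13.1 provides that "For all AE summary tables, a third group other than QD and BID dose group will be presented". The AE tables will therefore not line up exactly with the two groups of 20.

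Optionally, state the half-width on the t basis, as about SD/2.59 or 23.2 µm for an observed SD of 60 µm, so that it matches the t-based power statement.

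The cost is wording in two documents. The sample size and the 80% power figure do not change.
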